3.7.3 Adverse Events

All subjects will be assessed regularly for the potential occurrence of adverse events (AEs) from the date of informed consent to Visit 6. The incidence of treatment-emergent AEs (TEAEs) will be defined for new or worsening events from the first study treatment until 30

days after the last study treatment. Summaries will be conducted using MedDRA (version 21.1), by System Organ Class (SOC) and Preferred Term (PT).

An overview of adverse events for the ITT analysis set will be provided, summarizing the incidence of the following:

- Count of TEAEs;
- Subjects with TEAEs;
- Count of Treatment-emergent serious AEs (TESAE);
- Subjects with TESAE;
- TEAE by maximum severity;
- TESAE by maximum severity;
- Subjects with TEAEs that lead to discontinuation of study;
- Subjects with TESAEs that lead to discontinuation of study;
- Subjects with Related TEAEs;
- Subjects with Related TESAEs.

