12.2. Statistical Analysis of Efficacy Data

Efficacy summaries and analyses (where appropriate) will be based on the per protocol (PP) population of all treated subjects completing all treatment visits and Visit 8 with no major protocol violations. In addition, efficacy summaries may be presented for the intent to treat (ITT) population of all treated subjects with at least one post-baseline visit, using last observation carried forward (LOCF) to impute missing data. Efficacy endpoints will include summary statistics (frequency distributions, proportions, means, medians and standard deviations, as appropriate) by visit for the following parameters: Physician's DPN Lesion Assessment scale results per treated lesion, subject responders defined by Physician's DPN Lesion Assessment scale outcome, and changes from baseline treated lesion diameter.

Comparative inferential analyses will be conducted for data collected from subjects in Cohort 2. The primary efficacy comparisons between the two Cohort 2 treatment groups will be made on the per-subject mean change across all treated lesions in Physician's DPN Lesion Assessment scale from baseline to the final visit using an ANCOVA model. A similar secondary analysis will be performed on the pre-subject mean percent of treated lesions that are clear (PLA=0), and a similar analysis based on clear or near-clear lesions (PLA < 2). Another secondary analysis will be performed on subject responders with all treated lesion PLA scores = 0, as well as a similar analysis on subject responders with all treated lesion PLA scores < 2. An analysis of change from baseline lesion diameter will be conducted using the same methodology as the primary efficacy analysis. All analyses will be conducted at each post-baseline visit where possible. Summaries will also be presented by subject Fitzpatrick Skin Type.

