12.4. Statistical Analysis of Safety Data

Safety analyses will include descriptive statistics calculated on the safety parameters using the ITT population. The proportion of subjects with treatment-emergent adverse events will be tabulated and presented by study treatment group and Medical Dictionary for Regulatory Activities (MedDRA) System Organ Class. Vital signs, LSR scores and clinically relevant abnormal laboratory results will also be tabulated and presented.

Data from all treated subjects will be presented and summarized. Safety summaries by study treatment group will include listings by study medication of adverse events incidences within each MedDRA System Organ Class, and changes from pre-treatment values in vital signs. Adverse event summaries will be presented showing the proportion of subjects experiencing adverse events, both overall and by MedDRA System Organ Class.

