3.2 ANALYSIS POPULATION AND DISPOSITION OF SUBJECTS

3.2.1 Data Sets Analyzed

Per-protocol (PP) analysis set

All treated subjects completing all treatment visits and Visit 8 with no major protocol violations.

Intent-to-Treat (ITT) analysis set

Intent-to-Treat (ITT) analysis set includes all treated subjects with at least one post-baseline visit.

Safety analysis set

The Safety Analysis Set includes all treated subjects.

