3.3 DEMOGRAPHIC AND OTHER BASELINE CHARACTERISTICS

Demographic and baseline characteristics will be summarized for the PP and Safety analysis sets. Gender, race, ethnicity, and FST will be summarized with number and percentage presented for each category. Age, height, weight will be described with summary statistics (n, mean, Std Dev, median, minimum, and maximum).

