3.7 SAFETY ANALYSIS

The safety and tolerability of the investigational products will be determined by LSR, reported AEs, laboratory tests and vital signs. The Safety analysis set with actual treatment received (as opposed to randomized treatment) will be used for all safety summaries, unless otherwise specified.

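### SAP 3.7.3 places the adverse event overview on the ITT set, so a treated subject who leaves before Visit 3 can be missing from it; the likely impact is small

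*SAP*

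**What the plan says.** SAP 3.2.1 defines the two sets that matter here. For safety: "The Safety Analysis Set includes all treated subjects". For ITT there is a second condition: "Intent-to-Treat (ITT) analysis set includes all treated subjects with at least one post-baseline visit". SAP 3.7 then fixes the default: "The Safety analysis set with actual treatment received (as opposed to randomized treatment) will be used for all safety summaries, unless otherwise specified".

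SAP 3.7.3 specifies otherwise for one table: "An overview of adverse events for the ITT analysis set will be provided". That overview holds the counts of TEAEs and serious TEAEs, their maximum severity, and the rows for study discontinuation and relatedness. Nothing else in SAP 3.7 leaves the default. Exposure (3.7.1) names the Safety set; the LSR, SOC/PT, laboratory and vital-sign summaries name no set and fall to it.

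Protocol section 12 names only PP and ITT populations, with ITT defined in 12.2 as "the intent to treat (ITT) population of all treated subjects with at least one post-baseline visit". Protocol 12.4 makes two statements: "Safety analyses will include descriptive statistics calculated on the safety parameters using the ITT population", and then "Data from all treated subjects will be presented and summarized". SAP section 4, which lists departures from the protocol, does not mention the safety population.

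On a separate editorial matter, SAP 3.7.2 twice plans to tabulate LSR grades 1 to 4, once for subjects and once for lesions. The scale in Protocol Table 6 and SAP Table 5 runs from 0 to 3.

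**The concern.** Adverse events are collected from the first treatment, but ITT membership depends on a later visit. An early event that makes a subject leave can therefore also remove that subject from the table meant to show it. The overview is the only table for which the SAP lists serious, related and discontinuation rows, and those are the rows most exposed.

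The overview's denominator can also differ from that of the SOC/PT tables and of the baseline table. SAP 3.3 states: "Demographic and baseline characteristics will be summarized for the PP and Safety analysis sets", so no baseline table is planned for ITT. Apart from the overview, ITT serves only the primary efficacy endpoint with LOCF. Columns are small: 6 and 6 in cohort 1, and 8 and 16 in cohort 2 (24 subjects at 1:2).

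**Working it through.** The documents give no figure for this point, so there is nothing to reproduce. The definitions are compared first and the likely size is then estimated.

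**1. Can the two sets differ?** The Safety set requires treatment. ITT requires treatment and at least one post-baseline visit. They differ by the treated subjects with no post-baseline visit. Only untreated subjects are replaced (Protocol 5.5, SAP 2.2.4), so a treated early leaver stays in the Safety set.

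**2. Can such a subject have a recorded event?** Yes. Non-serious AE reporting starts with the first treatment (Protocol 10.1.3). Subjects are monitored for at least 20 minutes after treatment at Visit 2 (Protocol 10.2.1). For an AE withdrawal, the AE and termination CRF pages are completed (Protocol 10.2.3). The first scheduled post-baseline visit is Visit 3: Day 8 (+7) in cohort 1, Day 15 (+4) in cohort 2. The SAP does not say whether an unscheduled contact counts as a visit.

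**3. Dropout rate, from Protocol Table 1 (earlier A-101 trials).**
- Enrolled: 35 + 172 + 119 + 450 + 487 + 147 = 1410.
- Not completed: 1 + 3 + 3 + 4 + 8 + 8 = 27 (1.9%).
- Follow-up from Day 1 to end of study: 77 days (one trial, 35 subjects), 105 days (four trials, 1228 subjects), 147 days (one trial, 147 subjects).
- Person-days: 35×77 + 1228×105 + 147×147 = 153,244, counting every enrolled subject as followed to the end.
- Rate: 27 / 153,244 = 0.000176 per day.

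**4. Expected leavers before Visit 3.**
- Nominal Visit 3: 12×7 + 24×14 = 420 person-days; 420 × 0.000176 = 0.074.
- Latest window: 12×14 + 24×18 = 600 person-days; 600 × 0.000176 = 0.106.
- Chance of at least one, 1 − exp(−x): 7.1% and 10.0%.
- By group: Arm B 3.9 to 4.9%, Arm A 2.0 to 2.5%, cohort 1 1.5 to 2.9%.

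**5. Sensitivity.**

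| Assumption | Chance of at least one early leaver |
|---|---|
| Pooled rate, even over time | 7 to 10% |
| Lowest single-trial rate (4/450 over 105 days) | 3 to 5% |
| Highest single-trial rates (1/35 over 77 days; 8/147 over 147 days) | 14 to 20% |
| Early rate double the pooled average | 14 to 19% |
| One third of the 1.9% leave before Visit 3 | 21% |

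As an upper guide, suppose every non-completer left before Visit 3. The expected number is then 36 × 27/1410 = 0.69, and the chance of at least one is 50%. At the highest single-trial proportion (5.4%) these become 1.9 subjects and 86%.

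**6. Chance that the overview loses an event.** The leaver must also have had a TEAE. If 25%, 50% or 100% of early leavers did (assumption), the chance under the pooled rate is about 2 to 3%, 4 to 5% or 7 to 10%.

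**7. Effect on a column.** Dropping one leaver with a TEAE changes k/n to (k−1)/(n−1). If that subject has the column's only TEAE:

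| Column | Safety set | ITT |
|---|---|---|
| Cohort 1, one skin type | 1/6 (16.7%) | 0/5 |
| Arm A | 1/8 (12.5%) | 0/7 |
| Arm B | 1/16 (6.3%) | 0/15 |
| Total | 1/36 (2.8%) | 0/35 |

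**8. LSR grades.** Grade 4 does not exist, and grade 0 has no row in the two frequency tables. The shift tables show grade 0 only for lesions at treatment visits, for 4 of the 11 signs and both symptoms. For the other 11 − 4 = 7 signs, grade 0 appears in no listed table.

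**The case against.** The strongest reply is that nothing is contradicted. SAP 3.7 allows exceptions, SAP 3.7.3 makes one, and it follows the ITT sentence of Protocol 12.4. On that view the undocumented change is the move of the other safety summaries to a Safety set that protocol section 12 never names. This stands as far as it goes: the overview is a permitted exception. But the same protocol section also promises to summarize all treated subjects, and nothing explains why one safety table should use a different population from the rest.

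The second reply is that little is at stake. The SOC/PT summaries default to the Safety set, disposition gives discontinuations by reason, and the protocol synopsis names severity, relationship and discontinuation as AE endpoints in their own right. Subjects withdrawn for an AE continue to be monitored (Protocol 5.4 and 10.2.3), and that contact might count as a visit. The study is open label, its safety analysis is descriptive, and the sponsor no longer pursues the indication. All of this is fair and limits the consequence. However, SAP section 4 keeps full safety reporting in the abbreviated report, so the safety tables still need one consistent denominator.

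The third reply concerns the LSR item. It is a separate slip and adds nothing to the population point. Grade 0 can be obtained by subtraction where denominators and missing values are shown. The seven signs lack a shift table by design, because only four signs are graded 20 minutes after treatment. That is correct, so only the row labels need correcting.

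**Conclusion.** The concern holds. It is an unexplained exception rather than a contradiction, and it can exclude a subject because of the very event the table should count. The likely size is small: a 7 to 10% chance of any difference between the sets under the pooled rate, and a lower chance that an event drops out of the overview. No adverse event is lost from the report and no test or efficacy result changes. If everyone attends Visit 3, the two sets are identical.

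The estimate assumes that non-completion in six seborrheic keratosis trials, five of them vehicle-controlled, carries over to DPN, and that dropout is even over follow-up. Table 1 counts randomized or enrolled subjects, so some non-completers may never have been treated and the rate may be too high. Front-loaded dropout would push the figure up, as the sensitivity table shows.

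**What to change.** - **SAP 3.7.3:** name the Safety analysis set (all treated subjects, by treatment received) for the AE overview in place of the ITT set.
- **SAP section 4:** add one line stating that all safety summaries use the Safety set and that this settles the two statements in Protocol 12.4.
- **SAP 3.7.2 (editorial):** list grades 0, 1, 2 and 3 in both the subject-level and lesion-level sentences.

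These are wording edits to the SAP. They need no protocol amendment, new data or extra resources.

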3.7.4 Laboratory Tests

For each laboratory test, a summary will be provided for each visit. The absolute value and its change from baseline will be descriptively presented.

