9.3. Clinical laboratory sampling

Non-fasting blood samples for clinical laboratory analysis will be collected by a qualified staff member at Visit 1 and at Visit 8. Approximately 7.5 mL of blood will be collected for each chemistry sample and 3ml of blood will be collected for the complete blood count (CBC). These blood samples will be sent to a central laboratory for analysis. Refer to the study specific laboratory manual for instructions regarding handling of the blood samples and shipping instructions.

The following tests, at a minimum, will be conducted:

Chemistry Panel	Complete Blood Count
Albumin	Hematocrit
Alkaline phosphatase	Hemoglobin
Alanine aminotransferase (ALT)	Platelet count
Aspartate aminotransferase (AST)	Red blood cell morphology
Blood urea nitrogen (BUN)	Red blood cell count
Bicarbonate	White blood cell count
Calcium	White blood cell differential
Chloride	% & absolute
Creatinine	Basophils
Glucose	Eosinophils
Lactate dehydrogenase (LDH)	Lymphocytes
Phosphorus	Monocytes
Potassium	Neutrophils
Sodium	
Total bilirubin	
Total protein	
Uric acid	

The results of the clinical laboratory tests will be reported on the central laboratory's standard reports. These laboratory results will be sent to the investigator via fax/email. The investigator must review all laboratory reports in a timely manner and note NCS or CS to define the clinical significance of any result that is outside the normal range for the laboratory. The investigator must date and initial every laboratory report.

The investigator must review the Visit 1 laboratory results for all the measured analytes for each subject prior to Visit 2. The subject must not be enrolled to the study at Visit 2 if any of the Visit 1 results are outside normal range for the laboratory AND, in the opinion of the investigator, CS.

The investigator must report all laboratory results that are BOTH outside the normal range for the laboratory AND, in the opinion of the investigator, CS as medical history if found prior to the first study medication treatment or as an AE if found after the first study medication treatment begins.

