2.4.3.3 Laboratory Sampling

Non-fasting blood samples for clinical laboratory analysis will be collected by a qualified staff member at Visit 1 and at Visit 8. Approximately 7.5 mL of blood will be collected for each chemistry sample and 3ml of blood will be collected for the complete blood count (CBC). These blood samples will be sent to a central laboratory for analysis. Refer to the study specific laboratory manual for instructions regarding handling of the blood samples and shipping instructions.

Laboratory tests (minimum) are as follows:

Page **18** of **26** Date: 19-February-2019

Chemistry	Hematology
Albumin	Hematocrit
Alkaline phosphatase	Hemoglobin
Alanine aminotransferase	Platelet count
Aspartate aminotransferase	Red blood cell morphology
Blood urea nitrogen	Red blood cell count
Bicarbonate	White blood cell count
Calcium	White blood cell differential
Chloride	% & absolute
Creatinine	Basophils
Glucose	Eosinophils
Lactate dehydrogenase	Lymphocytes
Phosphorus	Monocytes
Potassium	Neutrophils
Sodium	
Total bilirubin	
Total protein	
Uric acid	

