3.1 GENERAL STATISICAL CONSIDERATIONS

Descriptive statistics (mean, standard deviation [Std Dev], median, minimum [Min], and maximum [Max]) will be used for continuous variables; number and percentage of subjects will be used for discrete variables. In general, the last measurement prior to the first dose of study treatment will be used as the baseline value. Nominal visits will be used for by-visit summaries and analyses.

All treatment group comparisons will be made at the 0.05 level using a two-sided hypothesis test, unless otherwise specified.

Summaries will be presented by each arm, ie, Cohort 1 FST 5, Cohort 1 FST 6, Cohort 2 Arm A, Cohort 2 Arm B, and Total (combining both cohorts subjects).

All tabulations of summary statistics, graphical presentations, and statistical analyses will be performed using SAS[®] Version 9.2 or higher.

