3.7.5 Vital Signs

Vital signs measurements include pulse rate, temperature, systolic blood pressure, and diastolic blood pressure. Measures at baseline and changes from baseline to post baseline visit will be summarized. The number and percentage of subjects with abnormal blood pressure will be summarized.

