4 CHANGES TO PLANNED ANALYSES

After communications with the FDA, the sponsor is no longer persuing a separate indication for in patients with DPN. Therefore, an abbreviated report will be produced for A-101-DPN-201. This abbreviated report will contain all the safety of a full report, but only the primary and key secondary efficacy analyses will be reported. As a result, the following descriptive statistics mentioned in the protocol will not be produced:

- Number and percentage of lesions by PLA score categories (clear, near-clear, small, and large): overall, separately for face or neck target lesions, separately for subjects with FST 5 and 6;
- Summary statistics on PLA score (mean of all lesions): overall and separately for subjects with FST 5 and 6;
- Summary statistics on percentage of lesions that are clear (PLA=0): overall, separately for face or neck target lesions, separately for subjects with FST 5 and 6;
- Summary statistics on percentage of lesions that are clear or near clear (PLA=0 or 1): overall, separately for face or neck target lesions, separately for subjects with FST 5 and 6;
- Number and percentage of lesions by location (face, or neck): overall and separately for subjects with FST 5 and 6.

Furthermore, the following hypothesis tests will not be performed:

- Change in percentage of lesions that are clear (PLA=0) from baseline evaluation to the last evaluation of the lesions ANCOVA model;
- Change in percent of lesions that are clear (PLA=0) or near-clear (PLA=1) from baseline evaluation to the last evaluation of the lesions ANCOVA model;
- Change in longest lesion diameter from baseline to the last lesion measurement ANCOVA model;

The protocol also states that efficacy summaries may be presented for the intent-to-treat (ITT) population using LOCF to impute missing data. The primary endpoint will be summarized and analyzed for the ITT population using LOCF to impute missing data, but none of the other efficacy endpoints will be summarized or analyzed for the ITT population.

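### SAP 3.7.4 does not carry over the protocol's tabulation of clinically relevant laboratory abnormalities, so a clinically significant result in the scheduled Visit 8 sample enters no planned incidence table

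*SAP*

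**What the plan says.** Protocol 12.4, on safety data, commits to a specific laboratory output: "clinically relevant abnormal laboratory results will also be tabulated and presented". Protocol 9.3 provides the raw material. The investigator classes every out-of-range result as clinically significant (CS) or not (NCS), and a CS result is to be reported as medical history before treatment or "as an AE if found after the first study medication treatment begins".

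SAP 3.7.4 is two sentences long. It plans a summary of each test at each visit and adds: "The absolute value and its change from baseline will be descriptively presented". SAP 3.1 gives the meaning: "Descriptive statistics (mean, standard deviation [Std Dev], median, minimum [Min], and maximum [Max]) will be used for continuous variables". The section has no count of out-of-range results, no count of CS results and no shift table.

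SAP section 4 sets out the departures from the protocol. All of them concern efficacy, and on safety it says: "This abbreviated report will contain all the safety of a full report".

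On timing, SAP 2.4.3.3 states: "Non-fasting blood samples for clinical laboratory analysis will be collected by a qualified staff member at Visit 1 and at Visit 8". SAP 3.7.3 treats an event as emergent only up to 30 days after the last treatment, and every item in its overview is a treatment-emergent event or a treatment-emergent serious event.

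**The concern.** Safety is part of the study's main objective, and the protocol named one laboratory output that says how many subjects had an abnormality that mattered. A reader of SAP section 4 would conclude that this output is intact, but SAP 3.7.4 does not specify it. A programmer working from the SAP would not produce it.

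This might be harmless if a CS laboratory result were counted elsewhere as an adverse event, since Protocol 9.3 sends it there. So the question is whether that route is open at the one time when post-treatment blood is drawn. If it is closed, the missing table was the only planned count of these results.

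**Working it through.** The plan states no figure to reproduce. The check is a comparison of sections followed by day arithmetic.

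**Laboratory output**

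| Source | Output |
|---|---|
| Protocol 12.4 | Tabulation of clinically relevant abnormal results |
| SAP 3.7.4 with 3.1 | Mean, SD, median, minimum and maximum of value and change |
| SAP section 4 | Only efficacy items listed as dropped; safety said to be complete |
| SAP 3.7.5, for contrast | Keeps a count of subjects with abnormal blood pressure |

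**Is the adverse event route open at Visit 8?**

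Inputs, from the schedule tables and SAP 3.7.3:
- Last possible treatment: Day 22 with a window of +4 in cohort 1; Day 29 with a window of +4 in cohort 2.
- Treatment-emergent window: 30 days after the last treatment.
- Visit 8: Day 106 ± 7, so Day 99 to Day 113.
- Visit 6: Day 50 ± 7, so Day 57 at the latest.

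Latest close of window = last treatment day + visit window + 30. Smallest gap = 99 − latest close.

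| Last treatment | Latest close | Smallest gap to Visit 8 |
|---|---|---|
| Cohort 1, Visit 4 | 22 + 4 + 30 = Day 56 | 99 − 56 = 43 days |
| Cohort 2, Visit 5 | 29 + 4 + 30 = Day 63 | 99 − 63 = 36 days |
| Cohort 2, Visit 3 | 15 + 4 + 30 = Day 49 | 99 − 49 = 50 days |
| Either cohort, Day 1 only | 1 + 30 = Day 31 | 99 − 31 = 68 days |

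For even the earliest in-window Visit 8 sample to be treatment-emergent, the last treatment would have to fall on Day 69 or later (99 − 30). The schedule allows Day 33 at most.

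Collection has also stopped. Protocol 10.1.3 and SAP 2.4.3.2 end it at Visit 6, at least 99 − 57 = 42 days before Visit 8. Footnote 18 of the schedule tables ends it at Visit 5, except for events related to local skin reactions, which a blood result is not. The two end points conflict, but the conclusion is the same under either.

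Under the SAP as written, then, a CS result in the scheduled Visit 8 sample is neither within adverse event collection nor treatment-emergent, and SAP 3.7.4 does not count it.

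**The case against.** The strongest reply is that the protocol left this to the SAP. The synopsis says that safety endpoints, laboratory tests included, are to be specified there and summarised descriptively, which SAP 3.7.4 does. That explains the form of the summary. It does not cancel the more specific promise in Protocol 12.4.

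A second reply is that nothing shows the table was removed. It is absent from the list of dropped items, and the statement that safety is complete could mean that the protocol commitment still stands. This is a fair reading, and the documents do not show a deliberate removal. Either way, the SAP does not specify the table.

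A third reply is that small columns hide little, and much of this stands. A reader might infer that laboratory safety is reduced to means, or that an extreme value would vanish. SAP 3.1 does not support that, because the minimum and maximum are shown. If, for illustration, one subject shifts by 5 SD, the column mean moves by 5/6 = 0.83 SD among 6 subjects and 5/16 = 0.31 SD among 16. What remains hidden is the number of subjects affected and whether the investigator judged the result significant. A modest but significant deviation could also go unseen.

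Finally, the closed adverse event route is partly a separate defect. A laboratory table would not reconcile Protocol 9.3 with the end of adverse event collection. That is correct, and it needs its own correction.

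**Conclusion.** The point holds as an undeclared mismatch between Protocol 12.4 and SAP 3.7.4. It has a practical consequence: no scheduled post-treatment laboratory result can reach an incidence count, because the sample falls at least 36 days after the treatment-emergent window and at least 42 days after the latest Visit 6.

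This rests on three assumptions:
- The protocol's clinically relevant (12.4) and clinically significant (9.3) are the same judgement.
- Treatments and Visit 8 fall within their windows.
- The claim covers the scheduled Visit 8 sample only. An unscheduled sample within 30 days of the last treatment could still yield a treatment-emergent event. A related serious event after Visit 6 still goes to the sponsor, but outside the treatment-emergent tables.

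Three stronger readings are not supported. With 24 subjects randomised 1:2, one subject is 1/8 = 12.5% of Arm A or 1/16 = 6.3% of Arm B, but these are reciprocals of arm size and say nothing about how often abnormalities occur. The protocol did not promise a low/normal/high shift table. Nothing in the documents suggests that a laboratory effect is likely. With the separate indication no longer pursued and the report abbreviated, the consequence is an incomplete safety account rather than a changed development decision.

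**What to change.** Add one table to SAP 3.7.4, on the Safety set by cohort and arm: the number and percentage of subjects with a Visit 8 result outside the normal range and judged CS, with the analyte identified. No baseline cross-classification is essential, because Protocol 9.3 bars enrolment with a CS result at Visit 1, so in an eligible subject a CS result at Visit 8 is new since screening. A shift table is optional. If the sponsor prefers not to produce the count, SAP section 4 should declare the omission.

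The cost is one standard table. The CS/NCS judgement is already required. If it exists only on the laboratory reports and not in the database, at most 36 Visit 8 reports need transcribing.

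Two related corrections should be handled separately:
- SAP 3.7.5 says "Vital signs measurements include pulse rate, temperature, systolic blood pressure, and diastolic blood pressure", which leaves out the respiration rate collected under SAP 2.4.3.4. Adding it is a minor consistency change.
- The duty to report CS laboratory results as adverse events (Protocol 9.3) must be reconciled with collection that ends at Visit 5 (schedule footnote 18) or Visit 6 (Protocol 10.1.3, SAP 2.4.3.2).
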